The protocol is being amended to add an electrocardiogram (ECG) assessment at Week 12, when steady state has been achieved, to allow Investigators to assess the effects of efpeglenatide on the heart earlier in the study.

Protocol amendment summary of changes table

Section # and Name	Description of Change	Brief Rationale
Section 1.3 Schedule of Activities (SOA)	An additional ECG assessment will be performed at the on-site visit at Week 12	Efpeglenatide is titrated in 2 mg steps every 4 weeks, so that the 4 mg dose will be achieved after 4 weeks and the 6 mg dose after 8 weeks of treatment. Therefore, the steady state level of the 6 mg dose will be reached around Week 12
Section 1.1 Synopsis, Section 3 Objectives and Endpoints, and Section 9.4.3 Other analyses	Change of anti-drug antibody (ADA) objective/endpoint from secondary objective/endpoint to tertiary/exploratory objective/endpoint Removal of Table 9 describing the statistical analysis of ADA	To harmonize the ADA endpoint with the other efpeglenatide Phase 3 clinical protocols Section 9.4.3 describes statistical analysis of secondary endpoints and the ADA endpoint has been moved to tertiary/exploratory endpoint

Section 5.1 Inclusion Criteria	Clarification of the documentation criteria for symptomatic myocardial infarction by adding a prior discharge hospital diagnosis and removal of cardiac enzymes	To clarify the documentation needed for history of symptomatic myocardial infarction
Throughout	Minor editorial and document formatting revisions	Minor, therefore have not been summarized

TABLE OF CONTENTS

PROTOCOL AMENDMENT SUMMARY OF CHANGES TABLE	3
DOCUMENT HISTORY	3
OVERALL RATIONALE FOR THE AMENDMENT	3
TABLE OF CONTENTS	5
LIST OF TABLES	8
LIST OF FIGURES	9
1 PROTOCOL SUMMARY	10
1.1 SYNOPSIS.....	10
1.2 SCHEMA.....	17
1.3 SCHEDULE OF ACTIVITIES (SOA).....	18
2 INTRODUCTION	22
2.1 STUDY RATIONALE.....	22
2.2 BACKGROUND	22
2.3 BENEFIT/RISK ASSESSMENT	23
3 OBJECTIVES AND ENDPOINTS	25
3.1 APPROPRIATENESS OF MEASUREMENTS	26
4 STUDY DESIGN	27
4.1 OVERALL DESIGN.....	27
4.2 SCIENTIFIC RATIONALE FOR STUDY DESIGN.....	28
4.3 JUSTIFICATION FOR DOSE	30
4.4 END OF STUDY DEFINITION.....	30
5 STUDY POPULATION	31
5.1 INCLUSION CRITERIA.....	31
5.2 EXCLUSION CRITERIA	33
5.3 LIFESTYLE CONSIDERATIONS.....	35

5.4	SCREEN FAILURES.....	35
6	STUDY INTERVENTION	36
6.1	STUDY INTERVENTION(S) ADMINISTERED.....	36
6.2	PREPARATION/HANDLING/STORAGE/ACCOUNTABILITY.....	37

1 PROTOCOL SUMMARY

1.1 SYNOPSIS

Protocol title: A Randomized, Double-blind, Placebo-controlled, Parallel-group, Multicenter Study to Evaluate the Effect of Efpeglenatide on Cardiovascular Outcomes in Type 2 Diabetes Patients at High Cardiovascular Risk

Short title: Effect of Efpeglenatide on Cardiovascular Outcomes (AMPLITUDE-O)

Rationale:

The Food and Drug Administration (FDA) requires new therapies for Type 2 Diabetes Mellitus (T2DM) to demonstrate that they do not result in an unacceptable increase in cardiovascular (CV) risk. The European Medicines Agency (EMA) reflection paper on assessment of CV safety of medical products recommends assessment of CV risk by either a meta-analysis of Phase 3 studies or a dedicated cardiovascular outcome trial (CVOT). The present study is a CVOT that has been designed to demonstrate the CV safety of efpeglenatide by assessing the noninferiority (NI) of efpeglenatide over placebo on 3-point major adverse cardiac events (MACE). If NI is established, superiority will also be tested.

Objectives and endpoints

Objectives	Endpoints
Primary	

To demonstrate that efpeglenatide 4 and 6 mg is noninferior to placebo on 3-point MACE in T2DM patients with high CV Risk	
Time to the first occurrence of any of the following clinical events, positively adjudicated by the Clinical Endpoint Committee (CEC):
CV deathNon-fatal myocardial infarction (MI)Non-fatal stroke
Secondary	

To demonstrate that efpeglenatide 4 and 6 mg is superior to placebo on 3-point MACE in T2DM patients with high CV risk	
Time to the first occurrence of any of the following clinical events, positively adjudicated by the CEC:
CV deathNon-fatal MINon-fatal stroke

Objectives	Endpoints

• To demonstrate that efpeglenatide 4 and 6 mg is superior to placebo on the expanded CV outcome in T2DM patients with high CV risk• To demonstrate that efpeglenatide 4 and 6 mg is superior to placebo on the composite outcome of new or worsening nephropathy in T2DM patients with high CV risk• To assess the safety of efpeglenatide 4 and 6 mg once per week (QW), both added to standard of care in T2DM patients with high CV risk	
• Time to the first occurrence of any of the following clinical events, positively adjudicated by the CEC:
- CV death- Non-fatal MI- Non-fatal stroke- Coronary revascularization- Hospitalization for unstable angina• Time to the first occurrence of any of the following clinical events:
- New onset or progression to macro albuminuria (>300 mg/g) accompanied by an albumin-to-creatinine ratio (UACR) value increase of $\geq 30\%$ from Baseline- Sustained $\geq 40\%$ decrease in estimated glomerular filtration rate (eGFR) from Baseline (for ≥ 30 days)- Chronic dialysis (for ≥ 90 days)- Renal transplant- Sustained eGFR < 15 mL/min/1.73 m² (for ≥ 30 days)• Adverse events (AEs), serious adverse events (SAEs), AEs leading to treatment discontinuation, AEs of special interest (AESI), AEs requiring specific monitoring• Safety laboratory values• Vital signs• 12-lead electrocardiogram (ECG)

Overall design:

This study is a Phase 3, multicenter, randomized, double-blind, placebo-controlled, parallel-group study in approximately 4000 T2DM patients at High CV Risk.

To be eligible for the study, patients must have T2DM with high CV risk and a glycated hemoglobin A1c (HbA1c) $> 7\%$ at screening, and the antihyperglycemic treatment must have been stable for 12 weeks prior to randomization, in the opinion of the Investigator.

Prior to randomization, the Investigator will be asked to pre-specify which therapeutic approach will be implemented should intensification of the background antihyperglycemic treatment be considered necessary during the study.

Patients who meet all eligibility criteria will come back for the randomization visit (Visit 3) and, if they are still eligible for the study, they will be randomized 1:1:1 to efpeglenatide 4 mg, efpeglenatide 6 mg or placebo. Randomization will be stratified by the current or potential future use of a sodium-glucose linked transporter-2 (SGLT2) inhibitor (Current use, Potential future use, Neither current nor potential future use).

Any antihyperglycemic treatment is allowed as background therapy (with the exception of glucagon-like peptide-1 [GLP-1] receptor agonists [RAs] and dipeptidyl peptidase-4 [DPP4] antagonists). For participants with HbA1c <7.5% at time of Screening, and who are treated with either insulin, glinide, or sulfonylurea, the doses of the glucose-lowering medications may be decreased at Randomization in order to prevent possible hypoglycemia. Antihyperglycemic therapy must not be modified for the first 12 weeks after randomization (other than for medical necessity). After the first 12 weeks post randomization and during the remaining double-blind treatment period, the management of glycemia will be left to the Investigator's and/or treating provider's judgment, informed by clinical guidelines and local/regional standards of care. Investigators will monitor the glycemic status and potassium levels of participants throughout the study. If treatment intensification is still considered necessary after dose increase of the background antihyperglycemic treatment, the Investigator can prescribe any other antihyperglycemic medication (according to its labeling), with the exception of a GLP-1 RA or a DPP4 inhibitor, that must not be used during the study.

Participants with a suspected renal event (reduction of eGFR) should have a repeat assessment of renal function 30 to 45 days following the onset of the event to confirm it is sustained.

If a participant discontinues treatment with investigational medicinal product (IMP) prematurely, the participant will undergo a premature End-of-Treatment (pEOT) Visit, but every effort will be made to have the participants return to the site at the time corresponding to their scheduled visits, until the end of study. There must be at least 6 weeks of post-treatment safety follow-up between the last IMP administration and the Study Closeout Visit for participants who discontinue IMP prematurely.

Participants will continue taking IMP after a CV or renal outcome has occurred. If the participant does not agree to continue taking IMP or to attend site visits, they will be contacted by telephone to inquire about safety status (including outcomes).

The study is event driven and will continue until 330 participants have at least one primary event (3-point MACE) positively adjudicated by the CEC. At that point all randomized patients have to be scheduled to return to the site for a Study Closeout Visit (timing and window will be communicated to the sites).

All randomized participants, including those who prematurely discontinued from IMP, will be followed from Randomization until the Study Closeout Visit or death, whichever comes first. A

post-treatment safety follow-up visit 6 weeks after the last dose of IMP will be implemented for patients still on study treatment at the Study Closeout Visit.

An independent Data Monitoring Committee (DMC) will review clinical study safety data and an independent CEC will review, assess and/or adjudicate all events of deaths, selected CV events (non-fatal MI, stroke, unstable angina leading to hospitalization, and heart failure leading to hospitalization), pancreatic events, and other selected AEs. An independent ophthalmologist expert will review in a treatment-blinded manner all reported AEs suspected to be diabetic retinopathy to assess the presence of retinopathy and the relationship of reported AE to IMP. See Appendix 1 ([Section 10.1](#)) for further details of study committees.

Number of participants:

Approximately 4000 patients will be randomly assigned to study intervention to end up with an estimated total of 330 participants with at least one positively adjudicated 3-point MACE event.

All randomized participants will be evaluable. See [Section 9.2](#) for details.

Intervention groups and duration:

The study will consist of 3 periods:

- A 2- to 3-week screening period
- A double-blind, placebo-controlled, multiple dose treatment period, including up to 8 weeks for dose titration
 - If, at any time during the study, a participant does not tolerate the study treatment, the IMP may be temporarily discontinued or if medically necessary, permanently discontinued.
 - If a maximum of 2 (two) consecutive doses are missed, the IMP can be restarted with the latest dose given; if 3 or more consecutive doses are missed, the IMP will be restarted using a new titration kit.
 - All IMP discontinuation should initially be considered as temporary unless permanent discontinuation is mandated by the protocol.
- A follow-up period of 6 weeks after the last dose of IMP

The estimated study treatment duration will be approximately 24 to 36 months, assuming approximately 12 months of recruitment, and approximately 24 months of treatment and follow-up after the last randomized participant.

Study interventions

Investigational medicinal products

Efpeglenatide

- Formulation: 0.5 mL of a sterile, non-pyrogenic, clear, colorless solution in a 1 mL disposable prefilled syringe (PFS). The two doses tested will be injected as 4 mg/0.5 mL

or 6 mg/0.5 mL. A third dose, 2 mg/0.5 mL will be used as the initial dose during the first 4 weeks of the titration phase

- Route of administration: Subcutaneous (SC) injection administered to the abdomen. Within this region, the site of injection should be changed (rotated) at each time to prevent skin reactions
- Dose regimen: once weekly on the same week day (eg, each Monday) at any time of the day
 - Dose will be titrated during Weeks 0 to 8 as shown in [Table 1](#).

Placebo

- Formulation: matching placebo (sterile, non-pyrogenic, clear, colorless solution in a 1 mL disposable PFS)
- Route of administration: SC injection administered to the abdomen. Within this region, the site of injection should be changed (rotated) at each time to prevent skin reactions
- Dose regimen: once weekly on the same week day (eg, each Monday) at any time of the day

Table 1 – IMP dose schedule

	Dose 1	Doses 2-4	Doses 5-8	Doses 9 onward
	Day 1	Weeks 1-3	Weeks 4-7	As of Week 8
Efpeglenatide 4 mg	2 mg	2 mg	4 mg	4 mg
Efpeglenatide 6 mg	2 mg	2 mg	4 mg	6 mg
Placebo	Placebo	Placebo	Placebo	Placebo

No posttrial access to study medication is foreseen.

Statistical considerations:

- **Analysis of primary objective:**

The primary analysis population will be the intent-to-treat (ITT) population that includes all randomized participants irrespective of compliance with the study protocol and procedures. Participants will be analyzed in the treatment group to which they are randomized.

The time to the first occurrence of the primary composite CV endpoint event (CV death, non-fatal MI, or non-fatal stroke) will be analyzed using Cox proportional hazards model with treatment (efpeglenatide 4 mg, efpeglenatide 6 mg, placebo), region, and randomization strata of current or potential future use of a SGLT2 inhibitor (Current use, Potential future use, Neither current nor potential future use) as the covariates. Participants who receive either 4 mg or 6 mg of efpeglenatide will be combined as one efpeglenatide treatment group when making comparisons using the appropriate contrast for the purposes of the primary analysis. The hazard ratio between

pooled efpeglenatide and placebo will be estimated along with the associated two-sided 95% confidence interval (CI).

The NI with the 1.8 and 1.3 margin will be demonstrated on the primary endpoint if the upper bound (UB) of the two-sided 95% CI is <1.8 and <1.3 , respectively.

Kaplan-Meier curves of the cumulative incidence rate will also be provided by treatment groups.

All participants will be followed up to the Study Closeout Visit or death, whichever comes first. The primary analysis will be based on the ITT approach that includes events occurring from randomization to the end of study, even after the participant has discontinued the study treatment. In the ITT approach, all randomized participants will be included and analyzed as randomized.

The analysis will be based on the positively-adjudicated CV endpoint events. Participants who have not experienced any of these primary CV outcomes as positively adjudicated by the CEC during the study will be censored at the last date with available information on the CV outcomes on or before the study end date for the participant.

- **Analysis of secondary objectives:**

If the NI with the 1.8 and 1.3 margin is demonstrated on the primary endpoint, the superiority of pooled efpeglenatide group (4 and 6 mg) vs placebo for the 3-point MACE will be tested in a hierarchical fashion.

The two other secondary efficacy endpoints will be analyzed using the same Cox proportional hazards model used for the analysis of primary endpoint with treatment (efpeglenatide 4 mg, efpeglenatide 6 mg, placebo), region, and randomization strata as the covariates.

The safety analysis will be conducted on the safety population that includes all randomized participants who have received at least 1 dose of double-blind treatment, regardless of the amount of treatment administered. Participants will be analyzed for safety analyses according to the treatment actually received.

All safety summaries will be descriptive; no statistical significance tests will be performed on safety data. These analyses will be based on the Safety Population. Treatment-emergent adverse events (TEAEs) are defined as AEs that developed or worsened or became serious during the period from the administration of first double-blind IMP dose treatments up to 30 days after the last administration.

Each of the two efpeglenatide treatment groups will be compared with the placebo group.

[figure not shown]
A pre-specified safety analysis will be performed in the subsets of participants on the background therapy of metformin + SGLT2, and on metformin + sulfonylurea. Safety summaries will be provided by treatment group for each of the subsets, including the summaries for AEs, SAEs, deaths, hypoglycemia, AESIs, and AEs requiring specific monitoring.

Data Monitoring Committee: Yes

See Appendix 1 ([Section 10.1](#)) for further details on Steering Committee, DMC, CEC, and Independent Expert.

1.2 SCHEMA

Figure 1 – Graphical study design

1:1:1 randomization, stratified by the current or potential future use of SGLT2 inhibitor (Current use, Potential future use, Neither current nor potential future use).

^a All randomized patients will be asked to return to the study site for a Study Closeout Visit when approximately 330 participants have at least one primary event (3-point MACE) positively adjudicated by the CEC
R: randomization; CEC: Clinical Endpoint Committee; SGLT2: sodium-glucose linked transporter-2

1.3 SCHEDULE OF ACTIVITIES (SOA)

	Screening		Intervention Period ^b							Participants who prematurely discontinued IMP		Participants who did not prematurely discontinue IMP		Notes
	Month		0	3	6	9	12/ 24/ ...	15/21/ 27/ ...	18/30/ ...					
Week	-3	-1	0	12	24	36	48/96/ ...	60/84/ 108/...	72/120/ ...					
Visit	1	2	3 R	4	5	6 ☎	7/11/...	8/10/12/... ☎	9/13/...	pEOT ^c	Study closeout ^d	Study closeout ^d	Follow-up	
Acceptable range (days)	+7 ^a	± 3 ^a		± 7	± 7	± 7	± 7	± 7	± 7				Closeout + 6 weeks	
Informed consent	X													
Inclusion and exclusion criteria	X		X											
Demography	X													
Physical examination	X		X				X			X		X		
Medical/surgical history	X													
Vital signs	X	X	X	X	X		X		X	X	X	X		
Height	X									X		X		
Body weight	X		X	X	X		X		X	X	X	X		
Ophthalmologic exam with fundoscopy	X ^e													

Month	Screening		Intervention Period ^b							Participants who prematurely discontinued IMP		Participants who did not prematurely discontinue IMP		Notes
			0	3	6	9	12/ 24/ ...	15/21/ 27/ ...	18/30/ ...					
Week	-3	-1	0	12	24	36	48/96/ ...	60/84/ 108/...	72/120/ ...					
Visit	1	2	3 R	4	5	6 ☎	7/11/...	8/10/12/... ☎	9/13/...	pEOT ^c	Study closeout ^d	Study closeout ^d	Follow-up	
Acceptable range (days)	+7 ^a	± 3 ^a		± 7	± 7	± 7	± 7	± 7	± 7				Closeout + 6 weeks	
12-lead ECG			X	X						X		X		Recording at Week 0 (Visit 3) should be obtained prior to first dose of double-blind IMP
Randomization			X											
Interactive response technology (IRT) contact	X	X	X	X	X		X		X	X	X	X	X	
Injection training/retraining and self-injection at site		X												
IMP dispensed			X	X	X		X		X					
IMP accounting				X	X		X		X	X		X		
IMP compliance				X	X	X	X	X	X	X		X		
Concomitant medication review	X	X	X	X	X	X	X	X	X	X	X	X		
AE and SAE review	←=====→													

	Screening		Intervention Period ^b							Participants who prematurely discontinued IMP		Participants who did not prematurely discontinue IMP		Notes
Month			0	3	6	9	12/ 24/ ...	15/21/ 27/ ...	18/30/ ...					
Week	-3	-1	0	12	24	36	48/96/ ...	60/84/ 108/...	72/120/ ...					
Visit	1	2	3 R	4	5	6 ☎	7/11/...	8/10/12/... ☎	9/13/...	pEOT ^c	Study closeout ^d	Study closeout ^d	Follow-up	
Acceptable range (days)	+7 ^a	± 3 ^a		± 7	± 7	± 7	± 7	± 7	± 7				Closeout + 6 weeks	
Laboratory assessments													Laboratory assessments performed at Week 0 (Visit 3) should occur prior to first dose of double-blind IMP	
HbA1c	X			X	X		X		X	X		X		
HBsAg and HCAb	X													
Hematology ^f	X		X	X	X		X		X	X	X	X	X	
Clinical chemistry ^g	X		X	X	X		X		X	X	X	X	X	
Lipid profile ^h	X			X			X			X		X		
Amylase, lipase, and calcitonin	X		X	X	X		X		X	X	X	X	X	
Urinalysis	X													Urine analysis: pH, glucose, ketones, leucocytes, blood/hemoglobin, protein.
Urinalysis (spot)	X		X	X	X		X		X	X		X		Urinary albumin-to-creatinine ratio (UACR) performed by spot urine
Pregnancy test (WOCBP only) ⁱ	X		X	X	X		X		X	X		X	X	

	Screening		Intervention Period ^b							Participants who prematurely discontinued IMP		Participants who did not prematurely discontinue IMP		Notes
Month			0	3	6	9	12/ 24/ ...	15/21/ 27/ ...	18/30/ ...					
Week	-3	-1	0	12	24	36	48/96/ ...	60/84/ 108/...	72/120/ ...					
Visit	1	2	3 R	4	5	6 ☎	7/11/...	8/10/12/... ☎	9/13/...	pEOT ^c	Study closeout ^d	Study closeout ^d	Follow-up	
Acceptable range (days)	+7 ^a	± 3 ^a		± 7	± 7	± 7	± 7	± 7	± 7				Closeout + 6 weeks	
Anti-efpeglenatide antibody sampling			X	X	X		X			X		X ^j		Samples will be drawn before the IMP dosing at the site

- a There must be not more than 3 weeks + 3 days between screening visit and randomization. In some cases, Visit 2 might be combined with Visit 3 (Randomization), as per Investigator's judgement, according to the patient's medical profile.
- b Additionally, in between each on site visit, starting after Visit 5, participants will be contacted by phone to collect endpoint events, IMP administration information, and safety data.
- c If a participant prematurely permanently discontinues treatment with IMP, the participant will undergo a pEOT Visit as soon as possible. Participants will then continue in the study with all study procedures/visits except those associated with IMP administration. Participants will continue to be followed after a CV or renal endpoint occurs irrespective of their treatment status. If the participant does not agree to site visits, he/she will be contacted by telephone to inquire about safety status (including hospitalizations and endpoints).
- d All randomized participants will be asked to return to the study site for a Study Closeout Visit when primary 3-point MACE are positively adjudicated in approximately 330 participants. The timing and window of this visit will be communicated to sites. For participants who previously prematurely permanently discontinued IMP, there must be at least 6 weeks between the last IMP administration and the Study Closeout Visit, the Study Closeout Visit will be the final study visit, and no further visits are planned.
- e Examination to be done unless exam has been performed within the last 6 months prior to randomization or within 3 months in patients with severe non proliferative diabetic retinopathy (NPDR)/ proliferative diabetic retinopathy (PDR)/Diabetic Macular Edema (DME) and documented. The ophthalmologic exam, whether completed within the last 6 months prior to randomization or at screening, will serve as the baseline assessment.
- f Hemoglobin, hematocrit, red blood cell (RBC) count with indices, white blood cell (WBC) count with differential, and platelets.
- g Total bilirubin (in case of values above the normal range, differentiation in conjugated and non-conjugated bilirubin), aspartate aminotransferase (AST), alanine aminotransferase (ALT), alkaline phosphatase (ALP), non-fasting plasma glucose, creatinine, estimated creatinine clearance, uric acid, sodium, potassium.
- h Non-fasting triglyceride, total cholesterol, high density lipoprotein (HDL) and low density lipoprotein (LDL); will be done once a year for the duration of the study after Week 24.
- i FSH and estradiol may be checked in case the status of post-menopausal cannot be decided. Serum beta-human chorionic gonadotropin (β-HCG) test at screening; urine pregnancy test for subsequent monitoring; if the urine test is positive, serum β-HCG should be tested for confirmation of the pregnancy. A monthly home urine pregnancy test should be performed by the patient between visits.
- j Participants with positive anti-drug antibody (ADA) at the end of study, and who experienced severe injection site or hypersensitivity reaction at whatever time during the study, will be asked to provide sample for anti-efpeglenatide antibodies assessments 4 and 6 months after the end of the treatment.

AE: adverse event; DME: diabetic macular edema; ECG: electrocardiogram; IMP: investigational medicinal product; HbA1c: glycated hemoglobin; HBsAg: hepatitis B surface antigen; HCAb: hepatitis C antibody; IRT: interactive response technology; NPDR: non proliferative diabetic retinopathy; PDR: proliferative diabetic retinopathy; pEOT: premature end of treatment; R: randomization; RBC: red blood cells; SAE: serious adverse event; WBC: white blood cells; WOCBP: woman of childbearing potential

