8.3.7 Disease-related events and other events not qualifying as AEs or SAEs

This study is designed to ascertain whether the following events (primary and secondary endpoints) are affected by efpeglenatide:

- CV death
- Non-fatal MI
- Non-fatal stroke
- Unstable angina requiring hospitalization
- New onset or progression to macro albuminuria (>300 mg/g) accompanied by a UACR value increase of $\geq 30\%$ from Baseline
- Sustained $\geq 40\%$ decrease in eGFR from Baseline (for ≥ 30 days)
- Chronic dialysis (for ≥ 90 days)
- Renal transplant
- Sustained eGFR < 15 mL/min/1.73 m² (for ≥ 30 days)

Because these events will be reported and analyzed as efficacy endpoints, they will not be reported according to the standard process for expedited reporting of SAEs even though the event may meet the definition of a SAE. They are waived from expedited regulatory reporting to Health Authorities and they will not be reported to pharmacovigilance except if the Investigator, according to his/her best medical judgment, considers these events as related to the IMP taking into consideration the patient's underlying disease. In that case, the Investigator will report it within 24 hours to the Sponsor. These events will be recorded on the corresponding CRF page in the participant's CRF within the appropriate time frame. An independent CEC will review and adjudicate all events of death, MACE, other selected CV events and other selected AEs. In addition, an independent DMC will collect, track and monitor information regarding the endpoints. The members, roles and responsibilities of the CEC and DMC will be described in a separate charter.

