#### **2.1.1 Study completer: subjects completed study closeout visit (in person or by phone) or has died while in study Demographic and baseline characteristics**

The baseline value (with the exception of serum creatinine and estimated glomerular filtration rate [eGFR]) is defined generally as the last available value prior to the first dose administration of double-blind IMP or the last available value on or before the date of randomization for patients

who were randomized but never exposed to IMP. For lab parameters, only central lab values should be used for baseline value derivation.

For serum creatinine and eGFR, baseline is defined as the average of all central lab values before the first dose of the double-blind IMP for those randomized and exposed or before randomization for those who were randomized but never exposed to double-blind IMP.

All baseline safety and efficacy parameters (apart from those listed below) are presented along with the summary statistics in the safety and efficacy sections ([Section 2.3.4](#) and [Section 2.3.5](#)).

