#### **2.1.3.2 Secondary efficacy endpoint(s)**

- Time to first occurrence of non-fatal stroke and death
- Time to the first occurrence of any of the following expanded CV events:
  - CV death
  - Non-fatal MI
  - Non-fatal stroke
  - Coronary revascularization
  - Hospitalization for unstable angina
- Time to the first occurrence of any of the following new or worsening nephropathy:
  - New onset or progression to macro albuminuria ( $>300$  mg/g) accompanied by an UACR value increase of  $\geq 30\%$  from Baseline
  - Sustained  $\geq 40\%$  decrease in eGFR from Baseline (for  $\geq 30$  days)
  - Chronic dialysis (for  $\geq 90$  days)
  - Renal transplant
  - Sustained eGFR  $<15$  mL/min/1.73 m^2 (for  $\geq 30$  days)

Low eGFR value and 40% eGFR decrease from baseline will be captured from dedicated eGFR page “Renal event-eGFR Decrease”. Participants with a suspected renal event (reduction of eGFR) should have a repeat assessment of renal function 30 to 45 days following the onset of the event to confirm it is sustained. For UACR increase, it will be captured and reported by lab. Chronic dialysis and renal transplant will be recorded in eCRF procedure pages: “Renal Event – Dialysis Procedure” and/or “Other Procedures”.

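### Baseline UACR is a single pre-dose value although two are scheduled and creatinine/eGFR are averaged; adding UACR to the averaging rule recovers a modest amount of precision at no cost in samples

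*Protocol*

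**What the plan says.** The spot-urine row of the Schedule of Activities (Protocol 1.3), annotated "Urinary albumin-to-creatinine ratio (UACR) performed by spot urine", is marked at Visit 1 (Week -3) and Visit 3 (Week 0) and is blank at Visit 2. The schedule also notes: "Laboratory assessments performed at Week 0 (Visit 3) should occur prior to first dose of double-blind IMP". Protocol 10.2 (Table 9) assigns the test to the central laboratory. Two comparable UACR values before treatment are therefore planned for each participant.

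In SAP 2.1.1 the baseline value "is defined generally as the last available value prior to the first dose administration of double-blind IMP". The only exceptions are two renal measures: "For serum creatinine and eGFR, baseline is defined as the average of all central lab values before the first dose of the double-blind IMP". UACR is not among them.

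Baseline UACR is used in two places:

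- **Renal composite.** This is the last test in the hierarchy (SAP 2.3.4.4). Its albuminuria component is worded "New onset or progression to macro albuminuria (>300 mg/g) accompanied by a UACR value increase of" at least 30% from Baseline (Protocol 8.3.7; same definition in SAP 2.1.3.2).
- **Exploratory change in UACR.** SAP 2.3.4.3 plans observed-data summaries by visit, with no test or model.

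On how the albuminuria event is identified, SAP 2.1.3.2 says: "For UACR increase, it will be captured and reported by lab". It does not say which baseline the laboratory uses.

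**The concern.** Two components of the same composite are defined relative to baseline and treat it differently. The 40% eGFR fall is measured from an averaged baseline, and the 30% UACR rise from one spot sample. The albuminuria component also has less protection afterwards: the eGFR criteria must be sustained for at least 30 days, with a repeat at 30 to 45 days, while no repeat UACR is specified. One post-baseline value set against one baseline value can decide an event.

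Sampling error in the baseline misclassifies some patients on the 30% criterion and adds noise to every change from baseline. The error arises before treatment and is the same in all arms, so what is at stake is precision and slight attenuation of the treatment contrast. The Screening value that would reduce this error is already collected, but it is not used as baseline whenever a Week 0 value exists.

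**Working it through.** **Plan's own figures.** Neither document states power or precision for the renal composite or for UACR change, so there is nothing to reproduce on this point. The nearest stated figure does reproduce. The blended HR is (0.25×3.7 + 0.75×4.4×0.85)/(0.30×3.7 + 0.70×4.4) = 0.890. With 330 events and 2:1 allocation, power at the 1.3 margin is 90.0% (stated: 90%).

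**Inputs.** From the documents: two pre-dose samples, the 300 mg/g and 30% thresholds, about 4000 patients at 2:1 (pooled active to placebo), and the visit weeks. The documents give no within-person variability of UACR, UACR distribution, drug effect on UACR or rate of progression. All of these are assumed below.

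**Step 1: who can be affected in the composite.** A value above 300 mg/g automatically satisfies the 30% rise if baseline is below 300/1.3 = 231 mg/g. Baseline error can therefore change event status only near or above that level. With median 28 mg/g and between-person log SD 1.7, about 11–12% of patients have a measured baseline above 231. With median 25 or 40, between-person SD 1.6 and within-person SD 0.4–0.7, the share is 9–16%.

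**Step 2: change in log UACR.** Let s² be the within-person variance, τ² the variance of true change and k the number of baseline samples. Then

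Var(change) = τ² + s²(1 + 1/k).

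If errors are independent, the error part falls from 2s² (k = 1) to 1.5s² (k = 2), a 25% reduction and the most that can be gained. With s² = ln(1 + CV²), the ratio of total variances is (1.5s² + τ²)/(2s² + τ²):

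- τ = 0, any CV: 0.75 (SE ratio 0.866)
- CV 100% (s² = 0.693), τ = 0.9: (1.040 + 0.81)/(1.386 + 0.81) = 0.84
- CV 30% (s² = 0.0862), τ = 0.9: (0.129 + 0.81)/(0.172 + 0.81) = 0.956 (SE ratio 0.978)

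The range is 0.75–0.96.

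**Step 3: the macroalbuminuria component, by simulation.** The runs used 4000 patients at 2:1, median 28 mg/g, log SD 1.7, treatment effect -0.25 log units, mean progression 0.10 log units per year (SD 0.25), visits at Weeks 12, 24, 48, 72, 96 and 120, and 300 runs per setting. An event is a first value above 300 mg/g that is also at least 1.3 times baseline. Reading A lets any patient have an event. Reading B excludes patients whose baseline is already above 300 mg/g. Entries are mean log-rank |Z|, and the last column is the ratio of squares minus 1.

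| CV | Reading | Last value | Geometric mean | Information gain |
|---|---|---|---|---|
| 30% | A | 4.70 | 4.94 | 10.5% |
| 30% | B | 3.75 | 3.89 | 7.6% |
| 50% | A | 4.08 | 4.22 | 7.0% |
| 50% | B | 3.49 | 3.65 | 9.4% |
| 70% | A | 3.90 | 3.99 | 4.7% |
| 70% | B | 3.49 | 3.62 | 7.6% |

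A second set of runs used median 25 or 40 mg/g, between-person SD 1.6, within-person SD 0.4–0.7, an 18% reduction on drug and seven samples. It gave gains of about 2–8% with independent errors and 1–6% with error correlation 0.3. A few settings at within-person SD 0.7 showed about zero. With true progression left out of the model, the gain reached about 17%, and 20% in one exercise.

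**Step 4: event counts.** Averaging does not remove chance crossings. Under reading A, mean events move from 374 to 381, 502 to 522 and 621 to 653. Under reading B they move from 200 to 198, 302 to 303 and 407 to 414. The benefit is better classification of events, not fewer of them.

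**The case against.** The strongest reply is that SAP 2.1.1 sets a clear, prespecified rule that favours no arm, and that no passage contradicts it. That is right: this is a better available choice, not an error of validity. In every illustration above, Z exceeds 1.96 under both baselines, so no illustrated conclusion changes.

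A second reply is that there may be a reason for preferring Week 0. A Screening UACR of at least 30 mg/g is one of six alternative risk factors for entry (Protocol 5.1, Table 4), so some Screening values are selected upward. This has some force but does not separate the two measures: Screening eGFR is also an eligibility criterion (Protocol 5.1 and 5.2), and eGFR is averaged.

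A third reply concerns the fix, and it stands. SAP 2.1.3.2 has the laboratory capture UACR rises, while SAP 2.3.4 and 2.3.4.2 analyse renal events as reported by the investigator. Changing the baseline definition alone might not alter any event.

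A reader might also infer more than the documents support:

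- **That the SAP averages the steadier measure and not the noisier one.** Neither document gives the variability of UACR or creatinine. The argument needs only non-zero within-person variation in UACR.
- **That baseline error feeds into event status generally.** Step 1 shows that it does not for most patients.
- **That the rule produces false events or tilts the comparison.** Both samples precede treatment, and Step 4 shows no reduction in crossings.
- **That the UACR-change result is at risk.** That endpoint is exploratory and only described, and the SAP does not state a log scale for it.

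**Conclusion.** The point holds as a minor efficiency loss. Two pre-dose central UACR values are planned, only the last serves as baseline, and the different treatment of creatinine and eGFR is unexplained.

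For the macroalbuminuria component, the loss is roughly 0–8% of log-rank information in most settings with true progression (two of the six tabulated settings give 9–10%) and up to about 17–20% without it. The loss in the full composite is smaller, because the eGFR, dialysis and transplant events are unaffected. Their share is not given, so the dilution cannot be quantified. For log UACR change, error variance would fall by at most 25%, and total variance to 0.75–0.96 of its present size.

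All these sizes rest on assumed UACR variability, distribution, drug effect and progression. Only the direction, the 231 mg/g threshold and the 25% ceiling (for independent errors) follow without those assumptions.

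**What to change.** In SAP 2.1.1, add UACR to the averaging exception. Baseline UACR would be the geometric mean of all central-laboratory values before the first dose, or before randomization for participants never dosed. If only one value exists, use that value.

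Then make the definition operative:

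- Derive the 30% criterion by programming from this baseline, or give the same baseline to the laboratory that flags UACR events.
- Use it for every UACR change and baseline summary.
- State how values below quantification enter the geometric mean, because the substitution rule in SAP 2.5.1 is declared not applicable to UACR.

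If the single-value rule is kept, state why UACR differs from eGFR.

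The cost is a short SAP edit, one derived variable, and either re-derivation of the UACR event flags or a revised laboratory instruction. No new samples or visits are needed. The change uses only pre-treatment data and should be made before unblinding.
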